## 2.0 STUDY OBJECTIVES

### 2.1 Primary Objective

- 2.1.1 Phase I: Characterize the safety and tolerability of intrapleural injection of talimogene laherparepvec alone and in combination with IV nivolumab
- 2.1.2 Phase II: Resolution ( $\leq 50$ cc drainage over three consecutive every other day drainages) of pleural fluid accumulation accompanied by patient-defined improvement in symptoms (dyspnea, cough and/or chest pain)..

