#### 4.1.1 Cohort Enrollment – Safety Run-in

Since this is the first time talimogene laherparepvec is being given in the intrapleural space (i.e. new route of administration), enrollment in safety run-in cohorts 1 and 2 will be staggered. Each subject will be required to complete the 7-week safety assessment period (i.e. 3 cycles of TVEC including the seroconversion cycle) of dose-limiting toxicity (DLT) before the next subject is enrolled. During the safety run-in period starting in Dose Level 1, patients will only receive intrapleural talimogene laherparepvec. The first dose of talimogene laherparepvec will be administered on Cycle 1, Day 1 at 4ml of  $10^6$  pfu/mL in 200 cc normal saline (intrapleurally) to seroconvert HSV-seronegative patients. Three weeks will be given for seroconversion. Subsequent doses of talimogene laherparepvec at 4ml of  $10^8$  pfu/mL will then be administered IP every two weeks (Q2W) starting on Cycle 2, Day 1 for up to 8 cycles. Patients will be assessed for dose limiting toxicity (DLT) related to IP administration of talimogene laherparepvec after they have completed at least 3 cycles (i.e. 7 weeks) of monotherapy. If  $\geq 2$  patients experience DLT, the study will be discontinued. If 1 patient out of 3 has DLT, 3 additional patients will be recruited and treated at the same dose level. If 0 out of 3 patients or  $\leq 1$  patient out of 6 has a DLT, the study will proceed to Dose Level 2. One week following completion of study therapy, subjects may proceed to systemic therapy per their decision with their physician.

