In Dose Level 2 (expected Phase II dose), the first 3 patients will receive both IP talimogene laherparepvec and IV nivolumab. The first dose of talimogene laherparepvec will be administered on Cycle 1, Day 1 at 4mL of  $10^6$  pfu/mL in 200 cc normal saline (IP) to seroconvert HSV-seronegative patients. Three weeks will be given for seroconversion. Subsequent doses of talimogene laherparepvec at 4ml of  $10^8$  pfu/mL + Nivolumab 240 mg IV will be administered every two weeks starting on Cycle 2, Day 1 for up to 8 cycles of therapy. Patients will be assessed for DLTs related to IP administration of talimogene laherparepvec after seroconversion and 2 cycles of combination therapy (i.e., 7 weeks of study treatment). If  $\geq 2$  patients experience DLT, the study will be discontinued. If 1 patient out of 3 has DLT, 3 additional patients will be recruited and treated at the same dose level. If 0 out of 3 or  $\leq 1$  patient out of 6 has a DLT in the dose level 2 cohort, the study will recruit additional patients in Phase II at this dose level and accrue a total of 24 patients as per study goal. All patients treated at dose level 2 in Phase I or Phase II, will be included in analyses of safety and efficacy. Safety stopping rules will ensure the safety of subjects receiving combination treatment in Phase II (see [Statistical Considerations in section 9.0.](#))

Subjects may continue talimogene laherparepvec for up to 9 cycles (i.e. alone or with nivolumab) until resolution of pleural effusion or they experience systemic disease progression. Subjects who have resolution of pleural effusion as defined by

the primary endpoints may continue nivolumab monotherapy per standard of care until disease progression (see section 4.2 for details on treatment and section 6.5.2).

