#### 4.1.3 Definitions of Dose Limiting Toxicities (DLT) – Safety Run-in

A DLT is defined as the development of any new non-hematologic treatment-related grade 3-5 adverse event during or up to 14 days following the third IP dose of talimogene laherparepvec. This results in a 7 week DLT period.

- All subjects with grade 4 DLT events will be permanently discontinued from the study
- All subjects with  $\geq$  grade 3 DLTs of myocarditis or pneumonitis will be permanently discontinued from the study
- I.e., if > 1 scheduled dose of talimogene laherparepvec is missed due to study treatment-related toxicity, talimogene laherparepvec will be permanently discontinued and this event will be considered a DLT

The following adverse events are considered exceptions:

- Grade 3 laboratory-defined events that are asymptomatic and resolve without permanent sequelae to grade 0-1 within a week (ex. a grade 3 LFT

elevation that occurs in the absence of symptoms, resolves to G1 within a week and does not result in any change in liver function).

- Alkaline-phosphatase elevation in patients with known bone metastases
- Pneumothorax, catheter-related complications or other intrapleural effects that are attributed to the standard of care catheter, disease state, or pre-existing medical problems that are not unexpected.
- G3 diarrhea or nausea that resolve to G1 or lower within 48 hours
- Any grade 3-infusion/hypersensitivity reaction symptoms that resolve to grade 0-1 with dose interruption, infusion rate reduction, or supportive care.
- Reactions attributed to nivolumab alone that would be expected in standard of care use may result in permanent cessation of treatment for an individual patient, but will not result in a DLT. Such a patient will be replaced. (Example: an infusion reaction of grade 3 to nivolumab consistent with that occasionally seen in standard of care use).
- Tumor lysis syndrome
- Any AE determined to be unrelated to study treatment
- Events related to disease progression/relapse

In addition, the following will be considered DLTs when treatment-related:

- Pleuritic pain refractory to opioid therapy
- Acute respiratory distress syndrome

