### 4.3 Dose Modifications/Delays

#### 4.3.1 Talimogene laherparepvec Dose Modifications/Delays

There will be no dose modifications allowed for talimogene laherparepvec during the study. Talimogene laherparepvec will be administered as described in section 4.2 above. Talimogene laherparepvec administration will either be withheld or permanently discontinued depending on the severity of event related to its administration. If a grade 4 DLT occurs, talimogene laherparepvec will be permanently discontinued. If grade 3 DLTs occur with talimogene laherparepvec administration as described in section 4.1.2 (Definition of DLTs), the next dose of talimogene laherparepvec will be withheld and will not be given until symptoms have resolved to  $\leq$  grade 1. If  $> 1$  scheduled dose of talimogene laherparepvec is missed due to toxicity, talimogene laherparepvec will be permanently discontinued.

Doses up to 4 mL at dose strength of  $10^8$  pfu/mL every 2 weeks (maximum cumulative dose of  $222.5 \times 10^8$  pfu) have been administered in clinical studies, with no evidence of DLT. The maximum cumulative dose of talimogene laherparepvec planned for this trial is 9 total administrations (including initial seroconversion dose). See section 5.1.6, for warnings and precautions related to talimogene laherparepvec administration. Patients may receive premedication with an anti-pyretic and anti-nausea medication (e.g., acetaminophen 500mg PO and prochloraperizine 10mg PO) prior to every talimogene laherparepvec injection.

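### The Dose Level 2 sentence in section 4.1.1 restricts DLTs to those related to the intrapleural virus, so it omits unexpected nivolumab-attributed events that the definition in section 4.1.3 counts

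*Combined protocol and SAP*

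**What the plan says.** Section 4.1.1 sets out both run-in cohorts. For Dose Level 1, virus only, it says: "Patients will be assessed for dose limiting toxicity (DLT) related to IP administration of talimogene laherparepvec". For Dose Level 2 it states that "the first 3 patients will receive both IP talimogene laherparepvec and IV nivolumab", and then: "Patients will be assessed for DLTs related to IP administration of talimogene laherparepvec after seroconversion and 2 cycles of combination therapy". The 3+3 limits follow in the same paragraph. Two or more patients with a DLT end the study, 1 of 3 adds 3 patients, and 0 of 3 or at most 1 of 6 opens Phase II.

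Section 4.1.3, headed as the DLT definition for the run-in, is worded differently: "A DLT is defined as the development of any new non-hematologic treatment-related grade 3-5 adverse event", within a 7-week period. It also treats as a DLT more than one virus dose "missed due to study treatment-related toxicity". Nine exceptions follow. One begins: "Reactions attributed to nivolumab alone that would be expected in standard of care use may result in permanent cessation of treatment". It goes on to say that such a reaction is not a DLT and that the patient is replaced.

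Section 4.1.4 describes the DLT assessment for virus given alone or with nivolumab and has no virus-only limit. The Phase I objective in 2.1.1 is: "Characterize the safety and tolerability of intrapleural injection of talimogene laherparepvec alone and in combination with IV nivolumab".

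Two references to the definition carry the wrong number. Section 8.2 cites 4.1.1. Section 4.3.1 cites 4.1.2 ("as described in section 4.1.2 (Definition of DLTs"), which is the catheter drainage section.

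**The concern.** The Dose Level 2 run-in decides whether the combination goes into Phase II. Its count should cover toxicity from either drug, apart from deliberate exemptions. The Dose Level 2 sentence uses the attribution phrase of the monotherapy cohort, where it was harmless because only one drug was given. Read literally in a two-drug cohort, it drops a category of event that 4.1.3 keeps.

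The exemption in 4.1.3 shows that this category was meant to count. There is no need to exempt expected nivolumab-alone reactions unless nivolumab-related events otherwise qualify. No sentence says which section prevails, and the virus-only phrase stands beside the decision limits. In a rule where one event triggers expansion and two end the study, the same patients could lead to different decisions depending on the section followed.

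**Working it through.** **1. Figures in the plan.** The protocol gives no DLT rate and no operating characteristics for the run-in, so there is no stated figure to reproduce.

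**2. The two sections side by side, for a Dose Level 2 patient.**

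| Event within the 7-week period | 4.1.1 read literally | 4.1.3 |
|---|---|---|
| Non-hematologic grade 3-5, related to the virus (alone or jointly with nivolumab), no exception applies | counted | counted |
| Expected reaction attributed to nivolumab alone | not counted | not counted; patient replaced |
| Hematologic event or another listed exception | not counted | not counted |
| Non-hematologic grade 3-5, attributed to nivolumab and not to the virus, unexpected | not counted | counted |

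The third row assumes that 4.1.1 takes the term DLT, with its exceptions, from 4.1.3 and adds only the attribution limit. The missed-dose clause in 4.1.3 is written as an elaboration of the definition. It also names no agent, and on that reading it does not widen the gap. The sections part only in the last row.

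**3. Consequence for the decision, with no rate assumed.**
- Two of the first 3 patients have last-row events. Under 4.1.3 there are 2 DLTs and the study stops. Under 4.1.1 the count is 0 of 3 and Phase II opens.
- One patient has a last-row event and another has a virus-related DLT. Under 4.1.3 the study stops. Under 4.1.1 the count is 1 of 3 and 3 patients are added.

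The count under 4.1.3 is never below the count under 4.1.1. A run-in that passes under 4.1.3 therefore also passes under 4.1.1, and every disagreement is in the less cautious direction.

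**4. Illustration with assumed rates.** Let *p* be the per-patient probability of a DLT counted under both wordings. Let *q* be the further probability of an event counted only under 4.1.3. Patients are taken as independent. For a counted rate *x*, the run-in passes with 0 of 3, or with 1 of 3 followed by 0 of 3:

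P(pass) = (1 − x)³ + 3x(1 − x)² × (1 − x)³ = (1 − x)³ + 3x(1 − x)⁵

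Under 4.1.1, x = p. Under 4.1.3, x = p + q. For p = 0.10:
- 4.1.1, x = 0.10: 0.729 + 0.30 × 0.5905 = 0.906
- 4.1.3, q = 0.02, x = 0.12: 0.6815 + 0.36 × 0.5277 = 0.871
- 4.1.3, q = 0.05, x = 0.15: 0.6141 + 0.45 × 0.4437 = 0.814

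The same calculation over a range of p:

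| p | 4.1.1 | 4.1.3, q = 0.02 | 4.1.3, q = 0.05 |
|---|---|---|---|
| 0.05 | 0.973 | 0.950 | 0.906 |
| 0.10 | 0.906 | 0.871 | 0.814 |
| 0.20 | 0.709 | 0.665 | 0.600 |

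Because disagreements run one way, the difference within a row is the probability that the two readings give different decisions. At p = 0.10 it is 0.906 − 0.871 = 0.035 for q = 0.02, and 0.906 − 0.814 = 0.092 for q = 0.05.

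**5. Likelihood of the starkest case.** The probability that at least two of the first 3 patients have a last-row event is 3q²(1 − q) + q³. This is about 0.001 at q = 0.02 and about 0.007 at q = 0.05.

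**The case against.** The strongest reply is that the documents already point to 4.1.3. Its heading and opening words mark it as the definition, whereas the sentence in 4.1.1 mainly schedules the assessment, and 4.1.4 repeats the assessment without a virus-only limit. This stands, and it is the main reason the point is minor. It does not remove the literal restriction from the paragraph that contains the decision limits.

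Second, the gap is narrow. Section 5.2.8 lists a broad set of known nivolumab reactions, which would tend to be expected and so exempt. Section 5.1.6 says the virus may itself cause immune-mediated events, including pneumonitis. An unexpected event under a new route and combination would be hard to assign to nivolumab with the virus excluded, and if it may be virus-related, both sections count it. This also stands, and it is why low values of *q* are used.

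Third, other safeguards exist: staggered enrollment, continuous monitoring by the principal investigator with DSMC review, a pause for any death within 30 days of study drug not due to progression, and a Phase II boundary based on grade 3-5 events attributed to therapy. They limit the harm but do not replace the run-in rule. Even if the first 3 patients are counted toward that boundary, its limit at n = 3 is 3, so two events would not reach it.

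Two stronger inferences are tempting. A reader might infer that 4.1.3 counts every treatment-related event, so that ordinary nivolumab toxicity falls into the gap. It does not: hematologic events and nine listed exceptions are excluded, among them expected nivolumab-alone reactions. A reader might also infer that the misnumbered references send people to the virus-only wording. Both references name their target as the DLT definition, and only 4.1.3 bears that heading. Moreover, the one in 8.2 serves the Phase II boundary and the one in 4.3.1 serves dose withholding. Neither sets the run-in count.

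**Conclusion.** Wrong as written; minor. The wording mismatch is certain. It affects the decision only through unexpected, non-exempt grade 3-5 events attributed to nivolumab and not to the virus, and where it does, it favours continuing.

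The size rests on assumed rates that the documents do not supply. For p from 0.05 to 0.20, the pass probability under 4.1.1 exceeds that under 4.1.3 by about 0.02 to 0.04 when q = 0.02, and by about 0.07 to 0.11 when q = 0.05. The lower values are more plausible, given the exemption. Larger shares of uncounted events would give larger differences, but nothing in the documents supports them.

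Nor does the text support a conclusion that nivolumab toxicity goes unmonitored. Sections 7.2 and 8.3 still have the events recorded and summarised. Only the run-in count is in question.

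**What to change.** In the Dose Level 2 paragraph of section 4.1.1, replace the virus-related qualifier so that patients are assessed for *DLTs as defined in section 4.1.3*. A plain citation is enough. Listing the agents again would sit awkwardly beside the nivolumab-alone exemption, which should stay.

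As housekeeping, correct the DLT-definition references in section 8.2 (now 4.1.1) and section 4.3.1 (now 4.1.2) to 4.1.3.

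Leave all the 4.1.3 exceptions, the 3+3 limits and the Phase II boundary values unchanged.

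The cost is one phrase and two section numbers, with no extra patients or procedures. The only downside is possibly a rare additional counted DLT at Dose Level 2.

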#### 4.1.2 TPC drainage

Tunneled pleural catheter drainage during both Phase Ib/II will occur as follows:

##### **Standard Drainage -**

Drainage will take place either in the subject's home or in a suitable clinical area. All drainages after placement should be performed using standard aseptic technique and, unless connected to an inpatient drainage device, should be performed using PleuX vacuum drainage bottles. All drainage volumes should be recorded in the subject's diary. The subject must contact the clinical site once he/she has drained <50mL on 3 consecutive drainages performed every other day.

##### **Study Drug Drainage -**

Following IP infusion of TVEC via the TPC, patients will allow the product to dwell for 24 hours. After 24 hours the patients will drain their TPC either fully or up to the point of symptom development (chest pain/pressure, progressive dyspnea, intractable coughing). Following drainage of the dwelled product, the patients will follow an every other day (QOD) drainage schedule. Patients will drain as fully as possible, stopping at the point of symptom development.

In the event patients develop dyspnea after IP infusion of TVEC they will be allowed to drain their TPC earlier than 24 hours.

#### 4.1.3 Definitions of Dose Limiting Toxicities (DLT) – Safety Run-in

A DLT is defined as the development of any new non-hematologic treatment-related grade 3-5 adverse event during or up to 14 days following the third IP dose of talimogene laherparepvec. This results in a 7 week DLT period.

- All subjects with grade 4 DLT events will be permanently discontinued from the study
- All subjects with  $\geq$  grade 3 DLTs of myocarditis or pneumonitis will be permanently discontinued from the study
- I.e., if > 1 scheduled dose of talimogene laherparepvec is missed due to study treatment-related toxicity, talimogene laherparepvec will be permanently discontinued and this event will be considered a DLT

The following adverse events are considered exceptions:

- Grade 3 laboratory-defined events that are asymptomatic and resolve without permanent sequelae to grade 0-1 within a week (ex. a grade 3 LFT

elevation that occurs in the absence of symptoms, resolves to G1 within a week and does not result in any change in liver function).

- Alkaline-phosphatase elevation in patients with known bone metastases
- Pneumothorax, catheter-related complications or other intrapleural effects that are attributed to the standard of care catheter, disease state, or pre-existing medical problems that are not unexpected.
- G3 diarrhea or nausea that resolve to G1 or lower within 48 hours
- Any grade 3-infusion/hypersensitivity reaction symptoms that resolve to grade 0-1 with dose interruption, infusion rate reduction, or supportive care.
- Reactions attributed to nivolumab alone that would be expected in standard of care use may result in permanent cessation of treatment for an individual patient, but will not result in a DLT. Such a patient will be replaced. (Example: an infusion reaction of grade 3 to nivolumab consistent with that occasionally seen in standard of care use).
- Tumor lysis syndrome
- Any AE determined to be unrelated to study treatment
- Events related to disease progression/relapse

In addition, the following will be considered DLTs when treatment-related:

- Pleuritic pain refractory to opioid therapy
- Acute respiratory distress syndrome

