### 8.2 Sample Size and Accrual

The null hypothesis that the true rate of resolution of pleural effusion is 45% (Van Meyer 2011) will be tested against a two-sided alternative. The null hypothesis will be rejected if 15 or more responses are observed in 24 patients. A one group chi-squared test with a 0.100 two-sided significance level will have 80% power to detect the difference between the null hypothesis proportion of 45% and the alternative proportion of 70% when the sample size is 24. This sample size was calculated using nQuery Advisor v7.0.

For the phase II portion, sequential boundaries will be used to suspend the trial if excessive numbers of patients experience an unacceptable toxicity. If the study reaches a stopping boundary, it may be terminated by the PI, or submitted to the Data and Safety Monitoring Committee with a description of the failures to date and a rationale for why the study should be continued. An unacceptable toxicity is defined as any grade 3-5 adverse event attributed to therapy (with exceptions; see section 4.1.1 Definitions of Dose Limiting Toxicities (DLT) – Safety Run-in). The accrual will be halted if the number of patients with unacceptable toxicity is equal to or exceeds  $b_n$  out of  $n$  patients with full toxicity follow-up (see table below). This is a Pocock type stopping boundary that assumes that an unacceptable toxicity rate of 0.20 is acceptable. If the true rate is equal to 0.20, the probability of crossing the boundary is 0.05.

Number of Patients, $n$	1	2	3	4	5	6	7	8	9	10	11	12	13	14	15	16	17	18	19	20
Boundary, $b_n$	-	-	3	4	4	4	5	5	6	6	6	7	7	7	8	8	8	8	9	9
Number of Patients, $n$	21	22	23	24	25	26	27	28	29	30										
Boundary, $b_n$	9	10	10	10	11	11	11	11	12	12										

Additionally, during the safety run-in (as indicated in section [4.1.1 of the protocol](#)) if  $\geq 2$  subjects experience a DLT at either dose level then the study will be discontinued.

Any death (other than death related to progressive disease) within 30 days of study drug administration will result in the study pausing whereupon the study will be placed on hold until an appropriate evaluation of the cause of death and a plan of correction, if necessary, is established.

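### Section 4.3.1 omits the permanent stop for Grade 3 myocarditis or pneumonitis that Section 4.1.3 imposes, leaving the virus re-dosing rule unclear for run-in patients

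*Combined protocol and SAP*

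**What the plan says.** Section 4.1.3 defines the dose-limiting toxicities of the safety run-in and attaches three permanent stops: for a Grade 4 DLT, for more than one virus dose missed through treatment-related toxicity, and for two named events from Grade 3 upward. On the last, subjects with at least "grade 3 DLTs of myocarditis or pneumonitis will be permanently discontinued from the study". The DLT window runs "during or up to 14 days following the third IP dose of talimogene laherparepvec".

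Section 4.3.1 governs dosing of the virus. After a Grade 3 DLT, "the next dose of talimogene laherparepvec will be withheld and will not be given until symptoms have resolved to" Grade 1 or lower. The permanent stops it states are a Grade 4 DLT and the missed-dose rule: if more than one "scheduled dose of talimogene laherparepvec is missed due to toxicity, talimogene laherparepvec will be permanently discontinued". It points to the DLT definition "as described in section 4.1.2 (Definition of DLTs"), but the heading at that number is "4.1.2 TPC drainage". Section 8.2 gives a different number again: "see section 4.1.1 Definitions of Dose Limiting Toxicities (DLT"). The definition is in 4.1.3.

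At Dose Level 1 there is no second drug: "During the safety run-in period starting in Dose Level 1, patients will only receive intrapleural talimogene laherparepvec" (Section 4.1.1).

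**The concern.** Section 4.3.1 is where staff would look when deciding whether to give the next virus dose. It repeats two of the three permanent stops in 4.1.3 and leaves out the third, so it reads as a complete list. For Grade 3 pneumonitis or myocarditis it therefore points towards withholding and waiting, where 4.1.3 requires a stop.

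What is at stake is a repeat intrapleural dose after a serious lung or heart event, in a trial that describes itself as the first to give this virus by that route. Section 5.1.6 lists pneumonitis among the immune-mediated risks of the virus. The nivolumab rules (4.3.2 and 4.3.2.4) stop nivolumab permanently for both events, but they do not govern the virus and do not apply at Dose Level 1.

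**Working it through.** The plan gives no figure to reproduce on this point. The check compares the two sections, then asks whether the scenario fits the calendar and how many patients it could reach.

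**1. The two sections side by side**

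| Event in a run-in patient | Section 4.1.3 | Section 4.3.1 |
|---|---|---|
| Grade 4 DLT | subject stops permanently | virus stops permanently |
| More than one dose missed through toxicity | virus stops permanently; counts as a DLT | virus stops permanently |
| Grade 3 myocarditis or pneumonitis DLT | subject stops permanently, resolved or not | virus withheld until Grade 1 or lower |

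Only the third row differs. Both rules can apply to the same patient: a treatment-related Grade 3 pneumonitis or myocarditis in the window meets the DLT definition, and neither event is a listed exception. At Dose Level 2, a reaction expected with nivolumab and attributed to it alone is not a DLT, so it falls outside both rules.

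**2. Calendar**

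Inputs: cycle 1 lasts 21 days and later cycles 14 days, with 9 doses in all (Sections 4.1 and 6.1). Counting dose 1 as day 0, doses fall on days 0, 21, 35, 49, 63, 77, 91, 105 and 119.

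- End of the DLT window: 35 + 14 = day 49, which is 7 weeks. Doses still possible after dose 3: 9 − 3 = 6.
- Next dose if one is missed after dose 1: 35 − 0 = 35 days later.
- After dose 2: 49 − 21 = 28 days. After dose 3: 63 − 35 = 28 days.

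A Grade 3 DLT that falls to Grade 1 or lower within those intervals meets the 4.3.1 condition for another dose.

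**3. Effect of a steroid taper, if one must finish first**

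Input: a taper of at least one month (4.4.1), taken as 28 to 31 days starting at once. The latest onset that still fits is the interval minus the taper.

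- After dose 1: 35 − 31 = 4 to 35 − 28 = 7 days.
- After dose 2 or 3: 28 − 31 = −3 to 28 − 28 = 0 days, so essentially none.
- The visit window of ±2 days shifts these limits by a few days.

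**4. Patients reached**

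Inputs: 3 to 6 patients at each of two dose levels, if both are completed (4.1.1). Run-in total: 3 + 3 = 6 to 6 + 6 = 12. The protocol gives no rate for these events; 1% to 5% is an assumption.

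- Both levels: 6 × 0.01 = 0.06 to 12 × 0.05 = 0.60 patients expected.
- Dose Level 1 alone: 3 × 0.01 = 0.03 to 6 × 0.05 = 0.30.

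These are upper figures at each assumed rate. They include Grade 4 events, which both sections stop, and slowly resolving events, which the missed-dose rule stops.

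**5. Trial decisions**

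The event counts as a DLT whichever section governs later dosing, so the 3+3 count is the same. The null rate, sample size and test in 8.2 do not depend on the re-dosing rule.

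**The case against.** The best reply is that both rules can be obeyed together. Section 4.1.3 is unconditional, while 4.3.1 sets a minimum condition before the next dose and never says that dosing must resume. A subject already off study has no next dose. Staff also cannot call an event a DLT without using the definition in 4.1.3, where the stop is printed, and 4.3.1 names that definition even though it misnumbers it.

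Much of this stands. A reader might infer that the protocol directs re-dosing after these events, or that the sections cannot be reconciled; the text supports neither. What remains is that nothing says 4.1.3 prevails, that 4.3.1 lists the other two stops and not this one, and that its section number leads to drainage instructions.

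Other safeguards narrow the gap without closing it:

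- Sections 4.5 and 4.7 remove patients for unacceptable toxicity or on the investigator's judgment. They apply to the virus but are discretionary.
- The taper in 4.4.1 is written around nivolumab. It would usually cost more than one virus dose if the steroid exclusion (3.2.6, carried forward by 4.4) were enforced, but 4.4 says only that discontinuation may be required.
- Section 5.1.6 does not name myocarditis among the listed immune-mediated risks of the virus, so at Dose Level 1 the practical concern is mainly pneumonitis.

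A reader might also count every planned patient, including Phase II, as exposed to the conflict. The documents do not support that: 4.1.3 is headed for the safety run-in and its window closes at week 7. Section 8.2 uses the DLT definition and its exceptions to define unacceptable toxicity for the Phase II boundary; it does not restate the individual stops.

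**Conclusion.** The omission is real and should be corrected. Read alone, 4.3.1 permits another virus dose after a resolved Grade 3 myocarditis or pneumonitis DLT with no more than one dose missed; 4.1.3 does not. The stricter reading is available, but the reader has to supply it.

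The reach is small: 6 to 12 run-in patients, most clearly the 3 to 6 at Dose Level 1, where no nivolumab rule applies. The expected number is at most 0.06 to 0.60 patients, resting on the assumed 1% to 5% rate and on both dose levels being completed. This concerns the safety instructions for individual patients; it does not affect the primary test or the 3+3 decision.

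**What to change.** Add to 4.3.1: *Grade 3 or higher treatment-related myocarditis or pneumonitis permanently stops talimogene laherparepvec.* Correct the DLT-definition reference to 4.1.3 in 4.3.1 (now 4.1.2) and in 8.2 (now 4.1.1).

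Wording the stop by event does more than reconcile the two sections. It also covers doses 4 to 9 and Phase II, where no explicit virus stop for these two events now exists. That part is a small added safety rule and should be presented as such in the amendment. Its downside is that a rare patient whose event resolves would lose later virus doses.

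The cost is a routine amendment. The amendment form marks therapy changes for IRB approval, and Section 9.6 requires that approval before implementation and review by Amgen. No visits, tests or patients are added.
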